6.2 Inclusion/Exclusion Criteria

Inclusion

- Age \geq 18 years
- Seen at internal medicine or family medicine clinic at GIMC or THC in last 12 months
- Left ventricular ejection fraction \leq 40%
- Prescription at IHS pharmacy in last 12 months

Exclusion

- Primary providers opted out of inclusion for that particular patient
- Hospice care

Eligibility: Eligibility of patients will be assessed by the study team based on the patient's medical record. However, as detailed, if provider feels patient is inappropriate for enrollment, they can also opt out of enrollment. Those who meet criteria will have a EHR message sent through the chart to the primary provider. Primary providers have 1 week to opt out. If they do not opt out, patient will be automatically enrolled and placed into a randomization cluster group.

Exclusion criteria have been kept to a minimum to ensure that the study can examine the effectiveness of using this heart failure care model within a 'real world' setting.

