9.1.4. Vital Signs

Most recent blood pressure, pulse will be extracted from the chart from the most recent clinic visit which is closest to enrollment.

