10. ADVERSE EXPERIENCE REPORTING AND DOCUMENTATION

10.1. Adverse Events

An adverse event (AE) is any untoward medical occurrence in a clinical investigation of a patient administered the treatment arm and that does not necessarily have a causal relationship with the treatment. An AE is therefore any unfavorable and unintended sign (including an abnormal laboratory finding), symptom or disease temporally associated with the administration of medication, whether or not related to that therapy. Adverse events will be recorded in the patient chart and a case report form (CRF.) Adverse events will be described by duration, severity, outcome, treatment and relation to GDMT if related (or unrelated). Our Data Safety Monitoring committee will perform an interim analysis of the data after 1 cluster enrollment/implemented at 30 days.

AE Severity

The National Cancer Institute's Common Terminology Criteria for Adverse Events (CTCAE) Version 3.0 should be used to assess and grade AE severity, including laboratory abnormalities judged to be clinically significant. The modified criteria can be found in the study manual. If the experience is not covered in the modified criteria, the guidelines shown in Table 1 below should be used to grade severity. It should be pointed out that the term "severe" is a measure of intensity and that a severe AE is not necessarily serious.

Table 1. AE Severity Grading

Severity (Toxicity Grade)	Description
Mild (1)	Transient or mild discomfort; no limitation in activity; no medical intervention or therapy required. The subject may be aware of the sign or symptom but tolerates it reasonably well.
Moderate (2)	Mild to moderate limitation in activity, no or minimal medical intervention/therapy required.
Severe (3)	Marked limitation in activity, medical intervention/therapy required, hospitalizations possible.
Life-threatening (4)	The subject is at risk of death due to the adverse experience as it occurred. This does not refer to an experience that hypothetically might have caused death if it were more severe.

Adverse Events Description

There are well known side effects of GDMT, which patients will be counseled on prior to initiation of therapy. Common side effects, or adverse events of therapy will be defined as in Table 2.

Table 2. AE Definitions

AE	Definition
Hypokalemia	K <3.0 mEq/L
Hyperkalemia	K >5.5 mEq/L
Hyponatremia	Na <130 mg/dL
Acute Kidney Injury	Increase in creatinine from baseline of >0.5
Hypotension	SBP <90 mmHg

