11.2. Demographic and Baseline Characteristics

The following demographic variables for each patient upon enrollment will be summarized: race, tribal affiliation, gender, age, BMI.

The following clinical variables and baseline characteristics will be summarized: most recent blood pressure and heart rate, baseline creatinine, baseline potassium, most recent brain

natriuretic peptide, if any heart failure hospitalization in last 12 months, ischemic or non-ischemic cardiomyopathy based on coexisting validated ICD for ischemic cardiomyopathy [ICD codes: ICD 9 414.8, ICD 10 I25.5]), comorbidities to include coronary artery disease, diabetes, chronic kidney disease (including stage, end-stage renal disease), atrial fibrillation, hypertension, hyperlipidemia, left ventricular ejection fraction on most recent echocardiography, and prior cardiac studies including coronary angiography, stress test, or cardiac MRI.

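### The adverse event definitions set no new-or-worse condition for five cut-off events and no end-stage renal disease exception for AKI, so findings that are not new can be counted, more readily in intervention time

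*Combined protocol and SAP*

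**What the plan says.** Section 10.1, Table 2 gives bare thresholds for five events: potassium below 3.0 or above 5.5 mEq/L, sodium below 130, SBP below 90 mmHg and heart rate below 50 bpm. Acute kidney injury is the only one of these laboratory and vital-sign events tied to the patient's own starting value: "Increase in creatinine from baseline of >0.5". It carries no unit, no time window and no renal exception. The Synopsis repeats these definitions. Section 5.3 repeats the laboratory ones but omits hypotension and bradycardia.

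Table 2 sits under a general definition of an adverse event as "any untoward medical occurrence in a clinical investigation of a patient administered the treatment arm", and as a sign, symptom or disease "temporally associated with the administration of medication, whether or not related to that therapy".

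Section 6.2 lists two exclusions, hospice care and "Primary providers opted out of inclusion for that particular patient"; the Synopsis adds unwillingness to take part. Section 6.2 also says "Exclusion criteria have been kept to a minimum". No renal, blood pressure, heart rate or laboratory exclusion appears. Section 11.2 summarises "chronic kidney disease (including stage, end-stage renal disease" among the baseline comorbidities.

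Baseline values are collected. For vital signs (9.1.4), "Most recent blood pressure, pulse will be extracted from the chart from the most recent clinic visit which is closest to enrollment"; 9.1.5 does the same for laboratory values. Neither sets a maximum age.

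Section 11.3 tabulates adverse events by treatment group, with severity and relationship to newly started therapy. A safety review takes place 30 days after cluster 1 is implemented.

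**The concern.** A safety endpoint should capture what happens after exposure begins. With bare cut-offs, a patient whose heart rate was already 48 or whose SBP was already 88 meets the definition at the next reading, although nothing has changed. The AKI rule avoids this by measuring from baseline, but it has a different gap: it applies unaltered to patients whose kidney disease is already end-stage, in whom a creatinine rise is hard to interpret as acute injury.

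Counts of this kind would do little harm to the comparison if both conditions were observed equally. The plan does not provide for that. Closer observation after implementation would turn stable abnormalities into an apparent excess on the model, or blur a real signal. The safety tables by treatment group and the early review of cluster 1 are exposed to this. The primary endpoint and the sample size are not.

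**Working it through.** The plan states no adverse event rate, no share of patients with end-stage renal disease and no numerical safety boundary, so there is no figure to reproduce. The check is a reading of the definitions, followed by illustrations on stated assumptions.

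**1. Can such patients be in the trial, and do the rules reach them?** Yes. Section 6.2 does not exclude them and Section 11.2 expects to describe end-stage renal disease. Neither Table 2 nor Section 5.3 has an exception or a new-onset condition.

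**2. Is capture equal in the two conditions?**
- Section 7.2: a home BP cuff is supplied once a patient reaches the intervention time point, and home BP and heart rate readings go into the EHR. Section 7.3: control patients receive usual care.
- Section 9.2: the study team orders metabolic panels after it has started a therapy.
- Section 10.1: the general definition refers to a patient in the treatment arm.
- Section 8.2: outcomes are pulled from the EHR by study members blinded to cluster, who need an explicit rule to separate new from old.

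More readings therefore arise after implementation.

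**3. Effect on a stable abnormality.** Assume 5% of patients have a persistent abnormality and all are measured after implementation. The rate shown under control is 5% × share measured:
- 100% measured: 5% control against 5% intervention, no spurious difference.
- 50% measured: 2.5% against 5%.
- 20% measured: 1% against 5%.

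**4. Effect on AKI.** Let d be the share with end-stage renal disease, f the share of those who meet the creatinine rule, and t the AKI rate in everyone else. Reported rate = (1 − d) × t + d × f. With t = 5%:
- d = 3%, f = 20%: 0.97 × 5% + 3% × 20% = 4.85% + 0.60% = 5.45%, about 5.5%.
- d = 10%, f = 20%: 4.5% + 2.0% = 6.5%.
- d = 3%, f = 80%: 4.85% + 2.40% = 7.25%, about 7.3%.
- d = 10%, f = 80%: 4.5% + 8.0% = 12.5%.

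All three inputs are assumptions. Restricting the endpoint to patients without end-stage renal disease returns the rate to 5%. With 100 patients, the denominator becomes 97 (d = 3%) or 90 (d = 10%).

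**5. The 30-day review.** With 80 to 100 patients in five clusters, cluster 1 has 80/5 = 16 to 100/5 = 20 patients. Section 4.4 implements it at time 0, so it has a baseline but no control period of its own (Section 4.3 says every cluster begins under control). If each patient has an assumed 2% to 10% chance p of a flag that is not a new event:
- Expected flags = n × p: 16 × 2% = 0.3 to 20 × 10% = 2.0.
- Chance of at least one = 1 − (1 − p)^n: 1 − 0.98^16 = 0.28 to 1 − 0.90^20 = 0.88.

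One flag in 20 is 5% of the cluster; two in 16 is 12.5%.

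**The case against.** The strongest reply is that the documents nowhere say that entry abnormalities are counted. An adverse event is an occurrence associated in time with medication, start and stop dates are recorded (the Adverse Events paragraph of Section 9.1), and the tables show relationship to newly started therapy. A heart rate of 48 that predates enrollment could be left out, or recorded as unrelated. That reading is fair and it stands as a possibility, but it is not a stated rule. Relationship coding describes an event after it has been counted; it does not remove it.

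Second, the AKI line is no evidence about entry abnormalities, since a high but stable creatinine does not meet it. That is right: it supports only the renal half, and the other half rests on the remaining rows of Table 2.

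Third, the size is unknown. The documents never mention dialysis, and listing a comorbidity does not show how many such patients will enter. Provider opt-out, the contraindication check in Section 7.2 and panels ordered only where appropriate may all reduce the numbers. This stands, which is why the illustration spans a wide range.

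Fourth, a reader might infer that the plan reports non-events as harm of the model. The documents do not support that. With equal capture, a stable abnormality shows in both conditions and cancels. An apparent excess needs unequal capture, which Sections 7.2, 7.3 and 9.2 make likely but do not quantify.

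Finally, the study manual, the supplement and the detailed SAP promised in Section 11 were not available and may contain a rule.

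**Conclusion.** The point holds as a gap in the definitions. Applied literally, Table 2 permits abnormalities present at entry, and creatinine changes in end-stage renal disease, to be counted as adverse events, and the pattern of measurement would place more of them in intervention time and in the cluster 1 review. It does not show that the investigators intend to count them, or that the safety tables will show false harm.

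The size cannot be found from the documents. On the assumptions above, a 5% AKI rate is reported as about 5.5% to 12.5%, and cluster 1 would carry 0.3 to 2.0 flags that are not new events. No safety boundary is stated that such a number would cross, but Section 11.3 allows stopping for safety, and one or two events weigh heavily in 16 to 20 patients. The change is worth making before the safety data are tabulated; nothing in the primary analysis depends on it.

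**What to change.** In Section 5.3 and Table 2, and in the detailed SAP, leave every cut-off unchanged and add three rules:

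1. Report the AKI endpoint only in patients without end-stage renal disease at baseline, with its own denominator. The others stay in the trial and in all other safety tables. State the creatinine unit and time window.
2. Count a potassium, sodium, SBP or heart rate event when the value meets the cut-off and is new or worse than a dated baseline, and list patients abnormal at baseline separately. Simply dropping patients already beyond the cut-off would hide real deterioration, and an old abnormal chart value could suppress a new event. The plan should define worse (a higher grade on the severity scale in Section 10.1 is one option), set a maximum age for the baseline, and say whether it is taken at study start or at implementation. Section 4.1 ties enrollment to implementation, so a value taken then would come after control time.
3. Apply the same rule in control and intervention time, and note in the safety tables that measurement frequency differs. Rules 1 and 2 remove non-incident findings; they do not equalise how often patients are measured.

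Section 5.3 should also list hypotension and bradycardia, as Table 2 and the Synopsis do.

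The cost is a few sentences, a slightly smaller AKI denominator and a little more analysis work. The baseline values are already collected, though they need dates.

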10.2. Serious Adverse Experiences (SAE)

An SAE is defined as any AE occurring at any dose that results in any of the following outcomes:

- death
- a life-threatening adverse experience
- inpatient hospitalization
- a significant disability/incapacity

Other important medical events may also be considered an SAE when, based on appropriate medical judgment, they jeopardize the subject or require intervention to prevent one of the outcomes listed.

10.2.1. Serious Adverse Experience Reporting

The study team will document all SAEs that occur (whether or not related to implementation) per Penn CER guidelines. The collection period for all SAEs will begin after the first patient cluster has enrolled and end 3 months post study period.

In accordance with the standard operating procedures and policies of the local Institutional Review Board (IRB)/Independent Ethics Committee (IEC), the site investigator will report SAEs to the Navajo Nation Human Research Review Board.

11. STATISTICAL METHODS AND CONSIDERATIONS

Prior to the analysis of the final study data, a detailed Statistical Analysis Plan (SAP) will be written describing all analyses that will be performed. The SAP will contain any modifications to the analysis plan described below.

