	mEq/L], hyperkalemia [K >5.5 mEq/L], AKI [defined as Cr increase >0.5 from baseline], Hyponatremia [Na<130 mg/dl], volume overload [urgent clinic visit/ ER visits for lower extremity edema, dyspnea, with clinical evaluation consistent with volume overload], hypotension (SBP <90mmHg), bradycardia (HR <50 bpm). Outcomes determined by review of medical, hospital, and billing records.
OTHER EVALUATIONS	None
SAFETY EVALUATIONS	Adverse events (to include hypokalemia [K<3.0 mEq/L], hyperkalemia [K >5.5 mEq/L], AKI [defined as Cr increase >0.5 from baseline], Hyponatremia [Na<130 mg/dl], volume overload [urgent clinic visit/ ER visits for lower extremity edema, dyspnea, with clinical evaluation consistent with volume overload], hypotension (SBP <90mmHg), bradycardia (HR <50 bpm).
PLANNED INTERIM ANALYSES	At 30-days after implementation for cluster 1, we will evaluate for safety. Serious adverse events will be monitored by the research team on an ongoing basis throughout the study.
STATISTICS Primary Analysis Plan	To assess the effectiveness of our intervention, measurement of rates of GDMT, including each specific medication of ACE inhibitors, ARB, ARNI, beta-blockers, MRA, SGLT2 inhibitors will be performed at baseline, at each cross-over time point, and at the conclusion of 6 months after the implementation of the intervention. The main analysis of our stepped wedge design will be based on a logistic mixed-effects model which will contain a random intercept to account for between-cluster variability, a fixed effect parameter for time, and a group indicator variable for the treatment for each subject and time to capture treatment differences over time.
Rationale for Number of Subjects	We anticipate there is approximately 100 patients with HFrEF actively engaged in care at GIMC. Our goal to enroll all patients given ethical concerns with withholding implementation to all patients.

SECTION 1: BACKGROUND

Statement of Purpose:

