8.2 Blinding of Intervention

Patients will be informed that they are enrolled in a new quality improvement program to get them on optimal therapy and thus will not be blinded to their randomization status or participation in this trial. Provider subjects will, obviously, not be blinded to the intervention as they are receiving the alert and will be consenting to participate in the study. We will engage in both pre-trial and periodic teaching and discussion with all participating care providers to inform clinicians about the nature of the study and to discuss specific factors that are being measured. The study team is not blinded to the cluster assignment as they are implementing the model. However, the outcomes will be pulled from the EHR from study members that are blinded to randomization/cluster status of the patient.

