11.3. Analysis of Primary and Secondary Endpoints

To assess the effectiveness of our intervention, measurement of rates of GDMT, including each specific medication of ACE inhibitors, ARB, ARNI, beta-blockers, MRA, SGLT2 inhibitors will be performed at baseline, at each cross-over time point. The main analysis of our stepped wedge design will be based on a logistic mixed-effects model which will contain a random intercept to account for between-cluster variability, a fixed effect parameter for time, and a group indicator variable for the treatment for each subject and time to capture treatment differences over time.

Safety and tolerability data will be summarized by intervention group.

Adverse event rates will be coded by body system and MedDra classification term. Adverse events will be tabulated by treatment group and will include the number of patients for whom the event occurred, the rate of occurrence, and the severity and relationship to newly started therapy.

Statistical Analysis: The primary analysis will utilize the intention to treat principle. A generalized linear model will be used to assess the relationship between randomization cluster status and the primary outcome. The model will use a log-link and independent correlation structure to allow for calculation of adjusted risk ratios. Statistical significance will be based on a P value of <0.05. For categorical secondary outcomes, a similar generalized linear modeling approach will be used. For continuous secondary outcomes, a generalized linear model will be used.

Assessment of contamination: Providers may learn to better treat heart failure as consistent with evidence-based therapies over time. Given we are not clustering by provider, but rather patients, it is possible that providers will take what is being implemented on their patient that is in an active implementation phase, and apply it to a patient in a non-active implementation phase. Therefore, there is a high risk of contamination. However, with the stepped wedge design, we will be able to also see how GDMT rates increase over the study period for those clusters who are not immediately in an active implementation arm. We will be able to better understand if increases in GDMT are related to the intervention or just due to increases over time due to improved knowledge of providers over time.

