Interim Analysis: We plan to have interim analyses at 30-days after enrollment of the first cohort. The interim analyses will allow us to stop the trial earlier for ethical considerations, unexpected adverse events. If there is high efficacy, we will continue the trial as all patients will be enrolled as per the stepped wedge design. Earlier stopping will be considered for the reason of safety and efficacy.

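### The SAP need not be locked before comparative data accumulate, two primary models are named, and no rule says who may see results by group

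*Combined protocol and SAP*

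**What the plan says.** **Timing.** Section 11 states "Prior to the analysis of the final study data, a detailed Statistical Analysis Plan (SAP) will be written describing all analyses" and adds "The SAP will contain any modifications to the analysis plan described below". No section gives a date, a sign-off, a lock before the interim or first crossover reading, or a condition that the author be blinded. Section 12.4 locks data at interim and final reports, not the SAP.

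**Access.** Section 8.2 says "The study team is not blinded to the cluster assignment as they are implementing the model". It continues that "the outcomes will be pulled from the EHR from study members that are blinded to randomization/cluster status of the patient". Section 12.1 has the Investigator review and verify all collected data, and 12.2 gives the PI the file linking data to patients. Sections 4.3 and 8.1 credit the PI with the randomization scheme, although 4.3 also has an independent statistician generate the clusters and their order.

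**Interim.** Section 10.1, repeated in 12.7, says "Our Data Safety Monitoring committee will perform an interim analysis of the data after 1 cluster enrollment/implemented at 30 days". The Synopsis says "At 30-days after implementation for cluster 1, we will evaluate for safety". The interim paragraph of 11.3 is written in the first person. It says that the trial would go on if efficacy were high, then ends "Earlier stopping will be considered for the reason of safety and efficacy".

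**Analysis.** Under 11.3, measurement of therapy rates "will be performed at baseline, at each cross-over time point". The same section first makes a logistic mixed model (random cluster intercept, fixed time effect, treatment indicator) the main analysis. It then gives the primary outcome a log-link generalized linear model with an independence structure and no stated time term. It promises adjusted risk ratios but lists no covariates.

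**The concern.** A 5% significance level means what it says only if the analysis was fixed before anyone choosing it could see comparative data. In a trial where the implementing team knows who is in which cluster, being earlier than the final analysis is not the same as being earlier than results. The stated rule would be satisfied by an SAP written after the interim and after every cluster's 30-day reading, choosing whichever of the two models in 11.3 looked better. Without a date that can be set against data access, a reader of the final report could not tell a principled choice from a result-driven one.

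**Working it through.** **1. Timeline.** Section 4.4 starts clusters 1, 2 and 3 at days 0, 30 and 60, and so on, so clusters 4 and 5 start at days 90 and 120. Adding 30 days, the primary endpoint falls due at days 30, 60, 90, 120 and 150. The interim is at day 30. All primary endpoint readings therefore exist by day 150, and the SAP may still be unwritten. A lock before the interim data cut would precede any planned look at results.

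**2. Who can see results by group.**
- Pointing to access: the team knows assignment (8.2); the Investigator reviews all data (12.1); the Synopsis and 11.3 describe the interim in the first person.
- Pointing away: extraction is blinded (8.2); 10.1 and 12.7 give the interim to a Data Safety Monitoring committee.
- On scope, the Synopsis limits the interim to safety, while 11.3 mentions stopping for efficacy.

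The documents neither say that the team sees comparative results nor forbid it.

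**3. The plan's own figure.** Section 11.4 claims more than 95% power for 25% to 50% with 4 clusters of 20 and five time points. With the Hussey-Hughes variance at an assumed ICC of 0, Var = Iσ²/(IU − W). Here I = 4, U = 4+3+2+1 = 10, W = 1+4+9+16 = 30, and σ² = [(0.1875 + 0.25)/2]/20 = 0.0109. Var = 4 × 0.0109375/10 = 0.004375, so SE = 0.0661. Then 0.25/0.0661 − 1.96 = 1.82, giving power 96.6%. The claim reproduces, and an earlier SAP lock does not affect it. What the lock protects is the 5% error rate.

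**4. Size of the choice.** If two valid tests were independent, reporting the better would give 1 − 0.95² = 9.75%. The two models share the same data, so simulation is more informative. All settings have no true effect and 5 clusters of 20 patients; two-sided testing is assumed. The logistic model was fitted with period effects and without the cluster random intercept, because patients are individually randomized to clusters and no cluster variance is expected. The log-link model had no time term, with robust standard errors. Usual-care rates, trends and correlations are assumptions, except the 25% starting rate in B, which matches 11.4.

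| Setting | Logistic | Log-link | Smaller p < 0.05 | Added over worse model |
|---|---|---|---|---|
| A1: 10% usual-care increase in every 30-day window (800 trials) | 5.1% | 4.6% | 7.1% | 2.0 |
| A2: usual-care increase falling from 15% to 6% over five windows (800 trials) | 4.5% | 6.1% | 8.1% | 2.0 |
| B: 25% on therapy, six time points, no trend, no patient correlation (1,000 trials) | 4.0% | 5.0% | 7.8% | 2.8 |
| B, trend of 2 points a month | 4.4% | 22.2% | 24.3% | 2.1 |
| B, latent patient correlation 0.5 | 10.6% | 5.7% | 12.6% | 2.0 |
| B, correlation 0.5 and trend | 12.1% | 24.8% | 30.0% | 5.2 |
| B, correlation 0.8 | 14.0% | 5.5% | 14.8% | 0.8 |
| B, correlation 0.8 and trend | 15.4% | 26.4% | 33.5% | 7.1 |

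A rerun of A1 and A2 with 4,000 trials gave 6.3% and 7.7% for the better of the two. Monte Carlo error in the 800-trial runs is not small: for 7.1% the 95% interval is 7.1 ± 1.96 × √(0.071 × 0.929/800), or 5.3% to 8.9%.

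**5. Reading the table.** In A2 the log-link model alone is already at 6.1%, so about 1.1 of the 3.1 points above 5% belong to that model. In the trend and correlation rows most of the excess comes from omitting time or ignoring repeated measures on a patient.

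**The case against.** The strongest reply is that the protocol is not silent. Section 11 already sets out an analysis in a dated protocol, and the SAP must contain any modifications, so a departure can be seen against the protocol. Amendments need prior written IRB approval (13.1). Extraction is blinded, and a committee is named for the interim. At day 30 only one of five clusters has reached its endpoint. The simulated inflation, moreover, measures the conflict between two models, which a lock date alone would not cure.

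Much of this stands. Modifications would be visible, but section 11 does not require them to be dated relative to data access, and the protocol does not say whether an SAP change counts as an amendment. Blinded extraction protects ascertainment; it does not blind whoever writes the SAP. Visibility also helps little when the protocol itself names two primary models, since choosing either is arguably no modification. The last objection is right, and the remedy must therefore also name one model.

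**Conclusion.** The point holds in a limited form, as a cheap improvement. The plan permits the SAP to be written and section 11 changed until the final analysis. It sets no lock before the interim or crossover readings, states no rule on access to accumulating results, and leaves two primary models open. Under scenarios A1, A2 and B without trend or correlation, taking the better model gives about 6% to 8% false positives against 5%. This rests on assumed usual-care rates and a simplified logistic model.

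A reader might infer more, and the documents do not support it:
- That the unblinded team has seen the interim and each crossover result. Knowing assignment is not seeing results by group, and access is simply not addressed.
- That the endpoint window and the ARNI-switch rule are also open. Section 5.1 fixes both; they would open only through a visible change.
- That the team records the fills that form the endpoint. It prescribes and documents medication changes (7.2); the endpoint rests on pharmacy fills (5.1).
- That the 12.6% to 33.5% figures measure result-driven choice. Across the simulation B rows, choice adds about 1 to 7 points over the worse model; the rest is the models' own error.

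**What to change.** In Section 11, replace the SAP deadline with wording such as: *The SAP, naming one primary model, will be finalised, signed and dated before the data cut for the 30-day interim analysis. Each later change will be dated and its reason given. Any change made after access to comparative results will be labelled post hoc.* If that date has passed, a statistician blinded to outcomes by cluster and period should finalise the SAP.

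In 11.3, keep one primary model and delete the other or label it a sensitivity analysis; list the covariates behind any adjusted estimate. State in one place who runs the interim and who may see interim and crossover results by group. Reconcile the Synopsis, 10.1, 11.3 and 12.7 on who conducts the interim and whether efficacy is in its scope.

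Cost: the SAP is written earlier, and some later changes must be reported as post hoc. Patient numbers, data collection and power are unchanged.
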